- b) **Block Quality:** Achieving an inability to sense cold ice-water in the cutaneous distribution of the brachial plexus trunk distal to the block within 30 minutes will be considered a **successful nerve block** preoperatively. If the patient has an inability to sense cold ice-water in the cutaneous distribution of the brachial plexus trunk distal to the block within 30 minutes will be considered a **successful nerve block** postoperatively. Anything less will be considered a **failed nerve block**.

12) Secondary Outcomes:

- i) Return of sensory function in the blocked area of the limb.
- ii) Return of motor function in the blocked area of the limb.
- iii) Post-op Nausea and vomiting before discharge
- iv) Nausea and Vomiting after discharge
- v) Changes in Blood Pressure (BP) in the PACU defined as any blood pressure +/- 20% of patient's baseline (either BP on admission if no clinic BP is documented, or most recent clinic BP as documented if that exists)
- vi) Changes in Blood Pressure in Second Stage defined as any blood pressure +/- 20% of patient's baseline (either BP on admission if no clinic BP is documented, or most recent clinic BP as documented if that exists)

Motor Block Scale Table

Muscle function level	Scale	
	Grade	Percent of normal
No evidence of contractility	0	0 %
Slight contractility, no movement	1	10 %
Full range of motion with gravity eliminated	2	25 %
Full range of motion against gravity	3	50 %
Full range of motion against gravity, some resistance	4	75 %
Full range of motion against	5	100 %

gravity, full resistance		
--------------------------	--	--

Definitions:

- a) Duration of Analgesic Block
 - i) Time from nerve block-needle withdrawal until the **time reported by the patient** that they first had awareness of painful sensation returning anywhere in the surgically operated upon area of the limb.
 - ii) Patient will be given a form to write time down as it occurs.
 - iii) They are expected to write down the date and time (hour and minute) they first perceive pain in the arm anywhere in the surgical area. (even if they wake up from sleep and first notice pain there).
 - iv) They will be telephoned within three days from the block to gather the data from the patient.
 - v) If they cannot find the form or did not write the date and time down, we will then use the date and time the patient recalls from memory.
- a) Duration of Sensory Block

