 - i) Time from nerve block-needle withdrawal until the **time reported by the patient** that they first had awareness of tactile (light touch) sensation returning anywhere in the blocked area. Patients will be given a form to write time down as it occurs. They are expected to write down the date and time (hour and minute) they first felt sensation return to the blocked area (even if they wake up from sleep and first notice sensation returned).
 - ii) They will be telephoned within three days from the block to gather the data from the patient.
 - iii) If they cannot find the form or did not write the date and time down, we will then use the date and time the patient recalls from memory.
- a) Approximate Duration of Motor Block
 - i) Time from nerve block-needle withdrawal until the **time reported by the patient** that, with the arm of the blocked extremity, they are able to **flex their bicep**. Patient will be given a form with a diagram and instruct them prior to sedation and placing the block. They will write the time down when they are able to achieve this outcome. They are to write down the date and time (hour and minute) they were first able to flex their bicep on the blocked limb.
 - ii) They will be telephoned within three days to gather the time from the form.
 - iii) If they cannot find the form or did not write the data down, we will then use the time the patient recalls from memory.
- a) Patient Satisfaction with the block
 - i) Patients will be asked the question: "Would you want a nerve block again if you needed a similar surgery in the future?" Yes / No

Secondary Outcomes Table

Did patient have nausea before discharge	
Yes	No
Did patient have vomiting before discharge	
Yes	No
Did patient have nausea after discharge (72 hours)	
Yes	No
Did patient have vomiting after discharge (72 hours)	
Yes	No
Did the patient have +/- 20% deviation of baseline Blood pressure in PACU from admission	
Yes	No
Did the patient have +/- 20% deviation of baseline Blood pressure in Second Stage Recovery from admission	
Yes	No

2) Study Background Information:

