- d)** Using sterile technique, cleaning the skin with tinted chlorhexidine and with the operators wearing caps, masks, and sterile gloves. The ultrasound probe will have a sterile sheath over it. Sterile ultrasound gel will be used.
- e)** With ultrasound guidance and nerve stimulator from 0.2 mA to 2.0 mA using a sterile Arrow 90mm insulated stimulation needle (StimuQuick).
- f)** If we are unable to stimulate the brachial plexus at the trunk level with the nerve stimulator, we will place local anesthetic in the region where the brachial plexus nerves are visualized using ultrasound based on the practitioner's experience with ultrasound-guided interscalene (brachial plexus trunks) nerve blocks.
- g)** Block start and end times will be recorded. Start time begins at block needle insertion. Stop time is the time of nerve block-needle withdrawal.
- h)** All patients will be monitored with blood pressure, pulse oximetry, ECG and have 2 liters per minute of oxygen administered by nasal cannula.
- i)** Emergency resuscitation equipment, intralipid, and emergency medications are present and immediately available for patient safety.

- j) Anesthesiologists will be present and/or immediately available should resuscitation efforts be necessary in the unlikely event of drug toxicity, cardiac arrest, or other adverse event.
- k) Any adverse outcomes (listed in “stopping rules” #23 below) will be reported to the Safety Monitors on the day it happens.
- l) The use of rescue blocks in the PACU will be counted and analyzed.

8) Statistics

- a) For our **primary outcome**, we will use ANOVA or Kruskall-Wallis test, after checking the normality of the data, to compare the duration of the analgesic block. If we find a difference among all 4 groups, we will use 2-sample t-test or Mann-Whitney U-test to explore differences between the individual groups.
- b) For our continuously distributed **secondary outcomes**, given that outcomes will be observed on every patient, we will use ANOVA or Kruskall-Wallis test. For outcomes with categories (nausea and vomiting and blood pressure), we will use the chi-square test. Similarly, we will explore the different group or groups using chi-square test or Fisher’s Exact test.
- c) We based our estimates upon Cumming’s, Candido’s and Casati’s previous studies and our clinical experience. We have estimated the expected additional analgesic time between the three groups.

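### Blood pressure is analysed only as a yes/no 20% deviation by unadjusted chi-square; recording the readings and adding a baseline-adjusted analysis of the lowest reading would recover lost information at little cost

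*Combined protocol and SAP*

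**What the plan says.** Section 12) Secondary Outcomes, v) and vi), defines the two outcomes by the same rule: "Changes in Blood Pressure (BP) in the PACU defined as any blood pressure +/- 20% of" the patient's baseline, and "Changes in Blood Pressure in Second Stage defined as any blood pressure +/- 20% of" that baseline. The baseline is "either BP on admission if no clinic BP is documented, or most recent clinic BP as documented if that exists". The rule covers any reading in the window and either direction. It does not say whether systolic, diastolic or mean pressure is meant.

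The Secondary Outcomes Table offers only Yes and No against "Did the patient have +/- 20% deviation of baseline Blood pressure in PACU from admission", with a matching line for second stage.

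Section 8) Statistics, b), groups blood pressure with nausea and vomiting: "For outcomes with categories (nausea and vomiting and blood pressure), we will use the chi-square test". Follow-up comparisons use chi-square or Fisher's exact test. For continuous secondary outcomes the same item says "given that outcomes will be observed on every patient, we will use ANOVA or Kruskall-Wallis test", but blood pressure is not among them.

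**The concern.** The 20% rule cannot be scored without a numeric baseline and numeric later readings, so the numbers must exist at the bedside. Section 7) Techniques, h), also says "All patients will be monitored with blood pressure, pulse oximetry, ECG". The analysis then uses the baseline only to set the cut. With a baseline of 130 mmHg the cuts are 0.8 x 130 = 104 and 1.2 x 130 = 156. A patient whose lowest reading is 106 and one who never leaves 131 are both scored No. A patient at 104 and one at 156 are both scored Yes.

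Blood pressure is one of the few tolerability outcomes the trial sets itself. If an adjuvant lowers pressure moderately, a chi-square on 40 per arm may well be non-significant, and that result could be read as evidence of haemodynamic safety.

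**Working it through.** **The plan's own figure.** There is none for blood pressure: no event rate, SD, target effect or power. The 40 per group (4 x 40 = 160) with 90% power in section 8) Statistics, d), follows an estimate of analgesic time and does not bear on this outcome. Only the arm size of 40 is used below. Every other input is an assumption.

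**Step 1. Information kept by a single cut.** Take one normally distributed percent change per patient. The efficiency of the yes/no outcome relative to the mean, for small shifts, is:

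- one-sided cut with event rate p: φ(c)² / [p(1−p)], where c is the normal quantile at 1−p;
- two-sided ±20% cut: [φ(b) − φ(a)]² / [P(1−P)], with a = (−20−μ)/SD, b = (20−μ)/SD and P the event rate.

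One-sided, p = 0.20: c = 0.842, φ(c) = 0.280, and 0.0784/0.16 = 0.49, a loss of 51%. The loss is 78% at p = 0.05 and 36% at p = 0.50.

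Two-sided, SD 15, μ = −10: a = −0.667, b = 2.0, P = 0.275, and (0.054 − 0.319)²/0.1995 = 0.35, a loss of about 65%. At μ = 0 the two tails cancel and nearly everything is lost. Over SD 8-20 and μ from 0 to −20 the loss runs from about 36% to about 100%.

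Pooling directions can also mislead. With a control mean of +10%, SD 15 and a 10-point lowering, the Yes rate falls from 27.5% to 18.2%, so a pressure-lowering drug appears to reduce deviations.

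**Step 2. Power at 40 per arm with several readings.** Simulation, 3,000 trials per setting, one adjuvant against plain, two-sided 5%, without the preceding four-group test:

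- baseline = 130 + person (SD 13) + reading noise (SD 7), so the baseline SD is √(169 + 49) = 14.8;
- later level = 130 − drop + 0.7 x person + a further SD of 9;
- four readings, noise SD 7 each; plain-arm drop 5, 10 or 15 mmHg.

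| Analysis | Extra 5 mmHg fall | Extra 8 mmHg fall |
|---|---|---|
| Chi-square, rule as written | 14-32% | 35-66% |
| Chi-square, falls only | 24-34% | 55-70% |
| ANCOVA, lowest reading on baseline | 50-52% | 88-90% |
| ANCOVA, mean reading on baseline | 53-55% | 91-92% |

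Monte Carlo error is up to about √(0.25/3000) = 0.9 points (one standard error), so differences of a point or two mean nothing. False-positive rates were about 4.5-6.3% for every method. With no plain-arm drop, the rule as written detects the 5 mmHg fall about 5% of the time, which is no better than chance.

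**Step 3. A different effect shape.** Same model, but the adjuvant causes one transient dip of 30-40 mmHg in 30% of patients, with a plain-arm drop of 0 to 10 mmHg:

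| Analysis | Power |
|---|---|
| Chi-square, falls only | 44-86% |
| ANCOVA, lowest reading on baseline | 61-80% |
| ANCOVA, mean reading on baseline | 14-23% |

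The mean does badly because a single dip is divided by four. The lowest reading holds up under both shapes. It is not best everywhere: with no plain-arm drop the falls-only chi-square has 66-86%.

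**The case against.** The strongest objection is that a threshold relative to the patient's own baseline answers a sensible tolerability question (did this patient have a marked deviation?) and that chi-square is a valid test of it. These are secondary outcomes and no power is claimed for them. All of that stands, and it is why the yes/no outcome should keep its test.

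A second objection is that a uniform shift favours a continuous analysis, whereas the plan targets any single excursion. This also stands in part. Step 3 shows that replacing the excursion test with mean pressure could itself hide brief falls. It does not defeat adding the lowest reading.

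Three stronger readings are tempting, and the documents support none of them:

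- A reader might infer that about half the information is lost. With a one-sided cut that needs an event rate near 21%. The plan gives no rate and uses a two-sided cut.
- A reader might infer that a real fall will probably be reported as no difference. Under the assumed model, 8 mmHg is detected 55-70% of the time counting falls only. The inference fits a 5 mmHg shift and some two-sided settings.
- A reader might infer that the readings are irretrievably lost. The documents show an outcomes table, not the full data form, and the numbers should be in the chart.

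**Conclusion.** The concern holds in a limited form. A numeric outcome with a numeric baseline is tested only as a two-directional yes/no by unadjusted chi-square, and no continuous analysis backs it up. Under the assumed uniform shifts, ANCOVA of the lowest reading raises power by roughly 20 to 55 points over the rule as written (5 mmHg: 50-52% against 14-32%; 8 mmHg: 88-90% against 35-66%). Counting falls only closes part of that gap, not all of it.

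These sizes rest on assumed SDs, four readings per patient, one agreed baseline, systolic pressure and a given shape of effect. None of these comes from the documents. The direction of the conclusion is firmer than its size. The change is worth making, but the trial's primary conclusion does not depend on it.

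**What to change.** 1. Add to the data form the baseline pressure and each PACU and second-stage reading, as numbers, with the number of readings.
2. In section 8) Statistics, b), add for each stage an ANCOVA of the patient's lowest systolic reading on baseline, with group as a factor. Report each adjuvant-minus-plain difference with a 95% CI (3 adjuvants x 2 stages = 6 estimates). Mean pressure can be a supporting summary only, because averaging hides brief falls.
3. Keep the 20% yes/no outcome and its planned test, and report falls and rises separately.
4. State which pressure component the 20% rule uses. Section 12), which prefers a clinic reading, and the Secondary Outcomes Table, which refers to admission, must be reconciled so that one baseline enters both analyses.

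The cost is a few more numbers copied from the chart and one more routine analysis per stage. Treatment, visits and sample size do not change. The downside is that a minimum depends somewhat on how many readings are taken, so that count should be shown by group. The form should be changed before data collection, to avoid going back to charts.

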Regional anesthesia in the ambulatory surgery center venue has been shown to decrease unwanted side effects of anesthesia and improve patient satisfaction with their operative care. Clinicians often seek ways to increase the duration of peripheral nerve blocks(1, 2) for outpatient surgery. This may enhance patient satisfaction and make for fewer unwanted post-operative side effects from anesthesia such as nausea and vomiting. One way to prolong regional anesthesia for patients is to send them home with a peripheral nerve catheter. (3-6) However, there can be multiple interventions associated with these. Catheter adverse conditions include infection, local anesthetic toxicity, catheter failure or dislodgement, infusion leakage, difficulty for the patient to remove their own catheter, and inadequate access to medical resources(7-9).

Adding adjuvants to local anesthetics has been a principle for some time.

Anesthesiologists have been adding epinephrine to spinal Marcaine to extend the spinal duration for years. Candido and Franco both added buprenorphine to upper extremity blocks and received triple the pain relief duration from their nerve blocks(10, 11). In addition Candido also added buprenorphine to a sciatic nerve block and received an additional 6 hours of pain relief(12). Cummings (13) of the Cleveland Clinic studied dexamethasone added to interscalene blocks and showed it added twice as much analgesic duration to the nerve block(14-16). Kim and Movafegh also studied adding decadron to local anesthetics and showed prolongation of sensory and motor block (16-17). Casati's research showed that adding Clonidine to Ropivacaine extended his sciatic femoral nerve block extended his pain relief for 3 hours(17-19). Although neither three adjuvant is FDA approved for perineural applications, they have been used in many studies without any detriment to patients(20). [name], of the University of

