Pittsburg has extensively studied these adjuvants on a laboratory level and has not shown any neural toxicity with these adjuvant additions(21, 22). Steroids have also been used in epidural injections for years without problems. Dexamethasone has even been used (23). Clonidine has been studied for epidural and intrathecal applications(24-26). It is FDA approved for use in epidural with chronic pain patients. Currently, we are using clonidine at the University of Iowa Hospitals and Clinics in our Acute Pain Service. We have it in our epidural solution for pediatric patients. Buprenorphine has also been studied for use intrathecally without problems(27). There is a study by an oral surgery department showing its safety and efficacy when added to oral nerve blocks(28).

Study Methods:

This study will be performed in the Ambulatory Surgery Center at the University of Iowa. All included patients will be undergoing orthopedic surgery on their shoulder for a surgery on the shoulder girdle, excluding the scapula. All regional blocks will be performed or directly observed and guided by the listed investigators. Blocks will be done using the interscalene approach to the brachial plexus. All the injections will be placed using simultaneous ultrasound guidance and a nerve stimulator technique with a previously published compressed air injection technique to limit injection pressure.(29, 30)

Per previous protocols involving anesthesia studies at University of Iowa Hospitals and Clinics (UIHC), those patients who are eligible will be given information on the day of surgery. A nurse not involved with the study will give the patient a card briefly informing the patient that they are eligible for a nerve block study. If the patient indicates their consent to hear more and possibly enroll in the study, a representative from the investigating team will *then* meet with the patient to explain the study and obtain informed consent.

An offer of regional anesthesia with or without intravenous sedation or general anesthesia will be provided to all patients regardless of their decision to participate or not. The techniques, practices, medications and use of ice-water to test blocks described in this protocol are currently used in common practice.

3) Inclusion Criteria:

Patients who have or are:

- a) Orthopedics service patients having **shoulder surgery**
- b) ASA class I, II, or III.
- c) Patients at least 18 years old but less than 71 years old.

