- d) Patients giving informed consent.

2) Exclusion Criteria:

Patients who have or are:

- a) An inability to cooperate during the block placement.
- b) Any neuropathy
- c) Diabetes
- d) Documented kidney disease
- e) Documented Hepatic disease

- f)** A lack of or inability to give informed consent.
- g)** Currently incarcerated.
- h)** Pregnancy

3) Consent:

- a) The study will be explained to the patient's satisfaction, their questions will be answered, and informed consent will be obtained from the patient after explanation of the risks, benefits, and alternatives.
- b) Once the patient has consented to the study, they will be included in the study and followed throughout.
- c) Patients with failed blocks will be included in the intention to treat analysis.
- d) If the block is unable to be placed due to infection at the site, poor visualization of structures with the ultrasound, inability to obtain study drugs within a reasonable time frame, or unexpected operator difficulty in placing the block, the patient will not be included in the intention to treat analysis and dropped from the study.

4) Randomization:

- a) A computerized random number generator will be used by a staff of the Anesthesia Department not involved with the study. They will create a randomized numbered sequence with four groups (A, B, C or D) that will be given to the pharmacy team. This will be used to fill study syringes in the sequence according to the randomization schema.
- b) The UIHC Pharmacy will compound the study drugs and will fill and label the coded study syringes.
- c) Coded study syringes must be created and delivered within 30 minutes of the physician's request.
- d) The Pharmacy will keep a record of which patient received each coded syringe and the solution they contained.
- e) They will be given to the practitioner at the time of block placement.
- f) Practitioners will perform the block using the pharmacy coded study drug.

5) Masking:

- a) Masking will be accomplished by using coded labels on the study mixtures.
- b) At the end of the study enrollment, information given to the statistical analyst will be blindly coded as groups A, B, C or D for data analysis.
- c) The Pharmacy will keep the group codes until after data analysis is complete.
- d) The anesthesiologist and nurse assistants will be masked to the study mixtures.
- e) Any assisting anesthesia Staff, Fellows, Residents, CRNAs, SRNAs, or medical students will be masked to the study mixtures.

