- d) Using the above parameters, a sample size is 40 per group with 4 total groups calculates to a sum of 160 subjects while using 90% power and 0.05 type I error rate.

9) Safety Monitoring:

- a) An Anesthesiology Faculty member who is not involved in the study will act as safety monitor and will review the data and any complications when half of the patients (n = 80) have been completed.

10) Stopping Rules:

- a) Any incidence of patient complications that occur with an incidence higher than published data for the following complications for peripheral nerve blocks will be enough cause for the Safety Monitors to stop the study(31, 32). Numbers in parentheses below are the highest incidence reported in the referenced article for peripheral nerve block complications. The highest incidence of complications was reported to be from the supraclavicular block, which we will not be performing. We are relying on results reported from our own regional anesthesia follow-up clinic. This is a clinic developed here to see patients with troublesome complications of peripheral nerve blocks. The complication rates have been reviewed and studied since the clinic inception over 4 years ago(33). We are erring on the side of caution by using higher complication rates of the supraclavicular adverse event reports.
- b) Published Peripheral Nerve Block Complication rates:
 - i) Seizure (26.3/10,000)
 - ii) Cardiac arrest (Code Blue) (15.9/10,000)

- iii)** Respiratory Failure (15.9/10,000)
- iv)** Peripheral neuropathy (32/10,000)
- v)** Patient death (15.9/10,000)

References:

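### Nausea and vomiting (8 b): stratifying by planned anaesthetic is a cheap improvement, useful if the anaesthetic given with the block varies and affects risk

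*Combined protocol and SAP*

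**What the plan says.** - **Study Methods**, on the anaesthetic: "An offer of regional anesthesia with or without intravenous sedation or general anesthesia will be provided to all patients". The sentence adds that this holds whether or not the patient joins the study. Every trial patient is to receive the interscalene block, so within the trial sedation or general anaesthesia would come on top of it. I found no passage that fixes this choice, records it or compares it between arms.
- **2) Study Background Information** credits regional anaesthesia with reducing anaesthetic side effects and hopes that longer blocks will mean "fewer unwanted post-operative side effects from anesthesia such as nausea and vomiting".
- **12) Secondary Outcomes** and the Secondary Outcomes Table list nausea and vomiting, before and after discharge, as yes/no items.
- **4) Randomization, a)**: "They will create a randomized numbered sequence with four groups (A, B, C or D) that will be given to the pharmacy team". No strata are described. Item c) has the syringes made up at the physician's request.
- **8) Statistics, b)**: "For outcomes with categories (nausea and vomiting and blood pressure), we will use the chi-square test". Differences between individual groups are then explored by chi-square or Fisher's exact test. No baseline factor appears.
- **8) Statistics, d)**: "a sample size is 40 per group with 4 total groups calculates to a sum of 160 subjects". The stated power is 90%, at a type I error of 0.05.

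**The concern.** The protocol itself ties nausea and vomiting to anaesthesia and leaves the anaesthetic open, but neither the randomization nor the test for these outcomes takes account of it. If some patients have general anaesthesia and others do not, and their risks differ clearly, two things follow. The variation between the two kinds of patient stays in the error term, so a real adjuvant effect on nausea or vomiting is harder to see. And with 40 per arm, an adjuvant arm and the plain arm may by chance hold different shares of general anaesthesia, which an unadjusted comparison cannot correct. Nausea and vomiting are part of the tolerability comparison of three additives, so a modest gain at almost no cost is worth having.

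**Working it through.** **The plan's own figure.** The 40 per group belongs to the primary outcome. No mean or SD is given, so it cannot be reproduced. Back-solving at 90% power and two-sided 0.05 gives a standardized difference of sqrt(2/40) x (1.960 + 1.282) = 0.725. The present point uses only the 40 per arm.

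**Inputs.** From the documents: 40 per arm, four arms, 0.05 level. Assumed, because the documents give nothing: the share q of patients under general anaesthesia (10-90%), the nausea or vomiting risk with it (20-50%) and without it (10%), and an adjuvant that multiplies risk by 1.8.

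**Step 1: how large a chance imbalance?** The SD of the difference in share between two arms is sqrt(2q(1-q)/40), which is 11.2 points at q = 50% and 8.9 points at q = 20% or 80%. By simulation, a gap of 20 points or more (8 of 40 patients) arises in 9% of single adjuvant-v-plain contrasts at q = 50%, 3.5% at 20% or 80%, and 0.5% at 10% or 90%.

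**Step 2: what does such a gap do?** Take risks of 40% v 10% and no drug effect. A 20-point gap shifts the expected difference between arms by 0.20 x (40 - 10) = 6 points. With an average risk of 25%, the standard error of the difference is sqrt(2 x 0.25 x 0.75/40) = 9.7 points, so the shift is about 0.6 standard errors. Among contrasts with a gap that large at q = 50%, unadjusted chi-square rejects in about 7%, 10% and 12% of cases for risks of 30%, 40% and 50% v 10%. The stratified test stays at about 5%. Over all trials, balanced or not, the pairwise chi-square error is about 5-6% and the four-arm error 4.6-5.1%.

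**Step 3: pairwise power.** I simulated 400,000 two-arm comparisons per cell. The number under general anaesthesia is binomial(40, q) in each arm. I compared chi-square with CMH, without continuity correction. The CMH statistic is (sum of [y - m n1/t])^2 / sum of [n1 n0 m (t - m)/(t^2 (t - 1))], summed over the two anaesthetic strata. Here y is events in the adjuvant arm, m all events, n1 and n0 the arm sizes and t = n1 + n0. The table gives the change in power, in points, from stratifying:

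| Share under general anaesthesia | 20% v 10% | 30% v 10% | 40% v 10% | 50% v 10% |
|---|---|---|---|---|
| 10% | -1.0 | -0.5 | +0.7 | +2.5 |
| 20% | -0.7 | +0.7 | +3.3 | +8.3 |
| 30% | -0.3 | +1.7 | +6.1 | +14.1 |
| 50% | 0.0 | +3.1 | +8.8 | +16.4 |
| 80% | +0.2 | +2.0 | +3.2 | +6.6 |
| 90% | 0.0 | +0.5 | +1.0 | +2.8 |

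In levels, at a 50% share, power goes from 26% to 26%, 36% to 39%, about 46% to 55%, and 61% to 77%. The right-hand column is the extreme: 1.8 x 50% implies a 90% risk in the adjuvant arm under general anaesthesia.

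**Step 4: the four-arm test that 8 b) runs first.** Shares were 20%, 50% and 80%. Risks without v with general anaesthesia were 10 v 20%, 10 v 30%, 10 v 40% and 20 v 50%. One arm's odds were multiplied by 0.25 or 3, with 60,000 repetitions per scenario. Stratifying changed power by -0.6 to +0.5 points at 10 v 20%, +0.3 to +3 at 10 v 30%, and about +2 to +6 at the two wider contrasts. The largest gain was 0.521 to 0.582 (50% share, 10 v 40%, odds ratio 3).

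**The case against.** The premise is inferred. The Study Methods sentence describes care on offer. It does not report the trial's anaesthetic mix or say who decides or when. If nearly everyone has the same anaesthetic, there is almost nothing to gain. The background section also does not compare block plus general anaesthesia with block plus sedation: its clause on nausea and vomiting is about longer blocks. Both points stand, and they make this a conditional point.

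The size depends on the inputs. The gain is zero or slightly negative when risks differ little or the anaesthetic is nearly uniform, and the large figures need an even split and a wide risk contrast. The pairwise figures also ignore the four-arm test that comes first. In addition, the simulation lets the stratifying type set the risk. An analysis by planned type gains less whenever the plan is departed from. All of this stands.

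A reader might infer that the planned chi-square is biased or has an inflated error rate. It is not and does not: randomization covers chance imbalance, and overall error stays near 5%. The 7-12% applies only to the minority of contrasts with a large gap.

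A reader might also extend the point to analgesic, sensory and motor duration, to blood pressure, or to age and ASA class as covariates. The documents link anaesthetic type to none of those outcomes and do not link age or ASA class to block duration. Any gain there would rest on an unsourced share of explained variance.

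What survives is the gap itself: a factor that the protocol associates with these outcomes is left open and then goes unrecorded and unused.

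**Conclusion.** The point holds as a cheap improvement to the analysis of nausea and vomiting, which are secondary outcomes. It is not a validity flaw, and the primary analysis is unaffected. The benefit depends on two things that the documents do not establish: that anaesthetic type varies appreciably between patients, and that risk differs clearly by type. Over the assumed ranges the change in power is about -1 to +16 points for an adjuvant-v-plain contrast and about -0.6 to +6 points for the four-arm test. The stratified test also keeps its error near 5% when the arms happen to be unbalanced.

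**What to change.** 1. Record the planned anaesthetic (block with or without sedation v general) before the coded syringe is requested.
2. In 8 b), prespecify for nausea and vomiting a CMH test, or logistic regression, stratified by planned anaesthetic. Keep the unadjusted chi-square and Fisher tests as supportive.
3. Report the anaesthetic mix by arm.

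Use the planned type, not the type given. The latter may depend on how the study block worked, and adjusting for something that follows allocation could introduce bias.

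The cost is one recorded item and a few lines in 8 b), settled before unmasking, with no extra patients. The downside is a negligible or slightly negative effect on power (about 1 point at worst in the scenarios above) if the anaesthetic is nearly uniform or the risks differ little.
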